## 6.2.3 Period 3: Post-Administration Collection (Visits 4A-4F) and Period 3 Follow-Up (Visit 5)

Investigators should ensure that subjects are contacted at least once per month by telephone or text message after Visit 3I to ensure subjects remain motivated to participate in the study and continue to complete their pDiary as well as to ensure the subject is available for their PAC2 and PAC3 periods.

#### 6.2.3.1 Visits 4A-4F: Post-Administration Collection

Subjects will participate in three post-administration data collection (PAC) periods.

Each PAC will take place over a 3-week period and will consist of 1 clinic visit at the start of the PAC period to provide the eDiary and Rescue Medication Package to the subject and 1 visit at the end of each PAC period to collect the eDiary. Subjects will record symptom scores, rescue medication use and ASS (where relevant) daily (in the morning) in the eDiary in the intervening 3-week period.

Investigators should contact subjects at the end of the first and second week of each PAC period by telephone or text message to remind and encourage subjects to complete the eDiary on a daily basis.

Investigators must review completion of eDiary data through the web portal and immediately contact any subject who has not completed the eDiary during a PAC period and seek to encourage the subject to resume completing the eDiary as soon as possible.

#### The PAC periods are:

- PAC1: Weeks 18-20 (±2 days) Visits 4A and 4B will occur on the first and last day, respectively. Visit 4B will take place at the same time as the Dosing Visit 3F. PAC1 may occur during a pollen period to which the subject has clinically significant symptoms.
- PAC2: Weeks 37-39 (±2 days), Visits 4C and 4D will occur on the first and last day, respectively. PAC2 may occur during a pollen period to which the subject has clinically significant symptoms.
- PAC3: Weeks 50-52 (±2 days), Visits 4E and 4F will occur on the first and last day, respectively. The PAC3 period must start after the end of the pollen period for all relevant seasonal allergens to which the subject has clinically significant symptoms

VERSION FINAL4.0 CONFIDENTIAL PAGE 52 OF 92

and must complete at least 1 week before the anticipated start date of the Spring pollen season for any allergen to which the subject has clinically significant symptoms.

If a subject requires medication for allergy symptoms during a PAC period they may take allergy rescue medications from the Rescue Medication Package provided in accordance with the Rescue Medication Plan (Appendix 3).

At the start of each PAC (Visits 4A, 4C and 4E), the following assessments will be performed:

- Vital Signs (sitting or semi-recumbent)
- Recording of AEs.
- Recording any changes in concomitant medications since last visit.
- The subject must be retrained on how to follow the Rescue Medication Plan (Appendix 3).
- Allergy rescue medication will be dispensed.
- Subjects will be reminded to check with the Investigator before they start any new medications other than their allergy rescue medication.
- A new pDiary will be issued.
- At the end of the visit, subject will be provided with their eDiary to record the following information on a daily basis, first thing in the morning, for the next 3 weeks:
  - o RSS using a 4 point categorical scale
  - o ASS
  - o Allergy rescue medication use

In addition, at the start of each PAC period, subjects will record their RSS using a VAS. This assessment will be based on the subject's assessments of their symptoms over the preceding week. Subjects will be asked to rate their allergy symptoms on a visual scale where 0 = no allergy symptom and 10 = my allergy symptom is the worst it could possibly be. This assessment will be recorded on the eDiary.

Note: Visit 4B at the end of PAC1 and the Dosing Visit 3F will take place at the same time and assessments that are duplicated at these two visits need to be made only once.

At the end of each PAC (Visits 4B, 4D and 4F), the following assessment will be performed:

- Vital Signs (sitting or semi-recumbent).
- Recording of AEs.

VERSION FINAL4.0 CONFIDENTIAL PAGE 53 OF 92

- Recording any changes in Concomitant Medication since the last visit, and any other allergy medication not recorded in the eDiary.
- Collect eDiary.
- Collect pDiary and transfer to eCRF:
  - Home environment changes (see Section 6.3.5).
  - o Concomitant medications.
  - o AEs
- Issue new pDiary at Visits 4B and 4D.

In addition, at Visits 4B, 4D and 4F the subject will complete the following assessments:

- o RQLQ (see Section 6.3.2).
- Spirometry (FEV1) [asthmatic subjects should not take their asthma medication for a minimum of 4 hours prior to spirometry].
- o ACT for asthmatic subjects.
- o PSQI

## 6.2.3.2 Period 3 Follow-Up (Visit 5)

A Period 3 Follow-up (Visit 5) visit will be conducted either at the same time as Visit 4F or as a separate visit no later than 10 days after the PAC3 period is completed. The following procedures will be conducted:

- Vital signs (sitting or semi-recumbent).
- Targeted physical examination (guided by findings at screening and emerging AEs).
- Blood samples for routine haematology and biochemistry.
- Blood sample for Der p and Der f specific IgE.
- Blood sample for biomarker analysis (OPTIONAL sub-study see Section 6.4.4.7)
- Blood sample for tryptase in any subject who has had a suspected anaphylactic response and is being withdrawn from the study.
- A dipstick urinalysis will be performed on the subject's urine.
- Urine pregnancy test (for FOCBP).
- Recording of any changes to concomitant medication since last visit.
- Recording of any AEs.
- Subjects will be asked to complete a Clinical Global Impression of Change in Rhinoconjunctivitis Symptoms.

VERSION FINAL4.0 CONFIDENTIAL PAGE 54 OF 92

## 6.3 Assessment of Efficacy

## 6.3.1 Measurement of RSS, ASS and Allergy Rescue Medication Use

Subjects will record their RSS using the 4 point categorical scale (reflective over last 24 hours), ASS and allergy rescue medication use on a daily basis, first thing in the morning, in an eDiary during the Baseline Allergy Evaluation, PAC1, PAC2 and PAC3.

Symptoms will be divided into nasal, non-nasal and asthma symptoms and rated for severity as described in Section 6.2.1.2.

Subjects will also record their RSS using the VAS (reflective over the past week) once at the beginning of the BAE and each PAC period.

## 6.3.2 Rhinoconjunctivitis Quality-of-Life Questionnaire

Subjects will complete the RQLQ at the end of the BAE and at the clinic visits at the end of PAC1, PAC2 and PAC3.

#### 6.3.3 Asthma Control Test

The ACT will be completed by asthmatic subjects at the end of the BAE and at the clinic visits at the end of PAC1, PAC2 and PAC3.

## 6.3.4 Clinical Global Impression of Change in Rhinoconjunctivitis Symptoms

Subjects will complete a Clinical Global Impression of Change in Rhinoconjunctivitis Symptoms at the Period 3 Follow-up visit (Visit 5). Subjects will rate their overall allergy symptoms at the end of the study relative to Baseline on a 7 point scale as follows:

- Very much better (0)
- Moderately better (1)
- A little better (2)
- Unchanged (3)
- A little worse (4)
- Moderately worse (5)
- Very much worse (6)

## 6.3.5 Home Environment (Exposure to Allergen)

Subjects will be asked to record any changes to their home environment in the pDiary. This will include changes to HDM control measures, such as, humidity, regular washing, regular vacuuming, installation of mattress and pillow encasings and significant changes to their home furnishing (e.g. removal of carpets). The Investigator will transfer this information into the eCRF. At the start of the BAE and at the end of the final PAC period, subjects will provide dust samples from their homes for analysis to confirm domestic HDM exposure and to measure levels of other perennial allergens such as cockroach and moulds. (Subjects in South Africa who do not have ready access to a vacuum cleaner will not be required to collect dust samples).

## 6.3.6 Pittsburgh Sleep Quality Index

The PSQI will be completed by subjects at the end of the BAE and at the clinic visits at the end of PAC1, PAC2 and PAC3.

## 6.4 Assessment of Safety and Tolerability

#### 6.4.1 Adverse Events

At each study visit, the Investigator will determine whether any AEs have occurred by asking non-leading questions. Adverse Event reporting begins from signed informed consent and ends at Visit 5.

An AE is any untoward medical occurrence. An AE can therefore be any unfavourable and unintended sign (including an abnormal laboratory finding), symptom or disease. An adverse drug reaction is defined as any noxious and unintended responses to a medicinal product related to any dose. The phrase "responses to a medicinal product" means that a causal relationship between a medicinal product and the AE is at least a reasonable possibility, i.e., the relationship cannot be ruled out. Treatment and placebo will be blinded in this study, so a causal relationship between treatment and an AE cannot be established before the data are unblinded.

All AEs must be fully recorded in the eCRF, from the time that a subject has provided signed informed consent to the time of their final study visit (although continued monitoring may be required for AEs ongoing at this visit).

When recording an AE, the following details should be given:

- Event observed (brief description using medical terminology);
- Start and stop dates and times;
- Severity (see below);

VERSION FINAL4.0 CONFIDENTIAL PAGE 56 OF 92

- Relationship to study medication (see below);
- Action taken (brief description);
- Outcome (see below);
- Serious (Yes/No).

#### An AE **does** include:

- Exacerbation of a pre-existing illness;
- Increase in frequency or severity of a pre-existing episodic condition;
- A condition detected or diagnosed after study start even though it may have been present prior to the start of the study.

#### An AE **does not** include:

- Medical or surgical procedures (e.g., surgery, endoscopy, tooth extraction, transfusion); the condition that led to the procedure is an AE.
- Pre-existing disease or conditions documented prior to the start of the study, which does not worsen.
- Elective surgery, social and/or convenience admissions previously arranged or anticipated before the start of the study and reported to the Investigator.
- Disease or disorder being studied or associated signs or symptoms provided these do not worsen/appear during treatment.
- Overdose of either study or concomitant medication without any signs or symptoms.
- Uncomplicated pregnancy

Adverse events will be recorded as they are reported, whether spontaneously volunteered by a subject or in response to questioning about well-being at each study visit. The subject will be questioned in a general way and no specific symptoms will be suggested. The questioning about AEs will cover the current visit and the period of time between the previous and current visit although subjects may report AEs occurring at any other time during the study. Follow-up of all AEs will continue until the overall clinical outcome is definitive. If any AEs have occurred, they will be recorded in the subject's medical record and transcribed to the eCRF. The Investigator must detail the symptom of the event, the onset of the event, the measures taken and the outcome, the date of disappearance or stabilisation. If known, the diagnosis should be recorded, in addition to the listing of individual signs and symptoms. The Investigator will assess each AE in terms of severity and relationship to study medication as indicated in the sections that follow.

#### **Severity**

Mild Noticeable to the subject, but does not interfere with their usual

activities. Usually does not require additional therapy, dose

reduction or discontinuation of medicinal product.

Moderate Interferes with usual activities, possibly requires additional therapy,

but usually does not require discontinuation of medicinal product.

Severe Incapacitating with inability to perform usual activities. May require

medical intervention and treatment and may require discontinuation

of medicinal product.

The Investigator will make a judgement regarding whether or not the AE was related to the study medication. The Investigator will evaluate any changes in laboratory values (including vital signs and 12-lead electrocardiogram and make a determination as to whether or not the change is clinically important and whether or not the changes were related to study medication. However, even if the Investigator feels there is no relationship to the study medication, the AEs MUST be recorded in the eCRF and the rationale for the judgement should be recorded in the medical notes.

#### **Causality**

Related: Any event that follows a reasonable temporal sequence from

administration of study treatment OR that follows a known response

pattern to the investigational drug.

(Any event that does not meet the criteria for unlikely or not related should

be classified as related)

Unlikely to be

related

Any event that does not follow a reasonable temporal sequence from administration of study treatment AND does not follow a known response

pattern to the suspected drug.

Not related Any event that starts before administration of study medication AND/OR

for which there is a clear alternative explanation.

#### **Outcome**

For each event, the following outcomes are possible:

- Recovered;
- Recovered with sequelae;
- Ongoing;
- Death;

VERSION FINAL4.0 CONFIDENTIAL PAGE 58 OF 92

• Unknown (appropriate follow-up to determine the outcome of all AEs will be undertaken and therefore "Unknown" should only be used as a last resort).

#### **Follow-Up of Adverse Events**

If any AEs are present when a subject completes the study or if a subject is withdrawn from the study, the subject will be followed up by telephone in 3-7 days. If the AE has still not resolved, additional follow-up will be performed as appropriate. Every effort will be made by the Investigator or delegate to contact the subject until the AE has resolved or stabilised. This should be documented in the subject's medical records. All AEs must be followed until resolution, until the condition stabilises, until the subject dies or is lost to follow-up. The Investigator is responsible for ensuring that follow-up includes any supplemental investigations that may be indicated, including (but not limited to) additional laboratory tests, histopathology or consultation with other health care professionals.

#### 6.4.2 Serious Adverse Events

A SAE is any untoward medical occurrence that:

- Results in death:
- Is life-threatening (subject is at immediate risk of death in the judgement of the Principal Investigator at the time of the event);
- Results in persistent or significant disability or incapacity;
- Requires hospitalisation or prolongation of an existing hospitalisation;
- Is a congenital abnormality or birth defect;
- Is a medically significant event;

Medical and scientific judgement should be exercised in deciding whether expedited reporting is appropriate in other situations, such as important medical events that may not be immediately life-threatening or result in death or hospitalisation, but may jeopardise the subject or may require intervention to prevent one of the other outcomes listed in the definition above. These should also be considered to be SAEs.

#### 6.4.2.1 Adverse events of Special Interest

Systemic Allergic Reaction (as defined by World Allergy Organization (WAO) Subcutaneous Immunotherapy Systemic Reaction Grading System, Appendix 4 [Cox et al., 2010]) are considered Adverse Events of Special Interest and should be reported expeditiously to the Sponsor in the same way as Serious Adverse Events.

If a systemic allergic reaction also meets any of the definitions of serious then it will also be

VERSION FINAL4.0 CONFIDENTIAL PAGE 59 OF 92

classified as a serious event and will be managed in the same way as any other serious event.

#### 6.4.2.2 Life-Threatening Adverse Event

The term "life-threatening" in the definition of "serious" refers to an event in which the subject was at risk of death at the time of the event; it does not refer to an event which hypothetically might have caused death if it were more severe.

## 6.4.2.3 Hospitalisation

This is defined as the subject being hospitalised overnight. Any pre-planned or anticipated inhospital visits should be documented in advance of the start of study medication administration and will be excluded from this category.

## 6.4.2.4 Subject Withdrawal

If the subject discontinues study medication administration due to a SAE and withdraws from the study, this should be reported using the SAE forms provided.

#### 6.4.2.5 Unexpected Adverse Event

An unexpected AE is defined as an AE, the nature or severity of which is not consistent with the applicable product information (i.e., the Investigator's Brochure).

#### 6.4.2.6 Reporting Serious Adverse Events/Expeditable Adverse Events

Investigators are obliged to notify, by fax, the contract Pharmacovigilance CRO, Icon plc (formerly Akos Ltd.), of all SAEs immediately (within 24 hours of the Investigator becoming aware of the event).

## SERIOUS ADVERSE EVENTS MUST BE REPORTED BY PHONE, FAX OR EMAIL TO ICON IMMEDIATELY

(NO LATER THAN 24 HOURS OF THE INVESTIGATOR BEING NOTIFIED)

[name] (Phone for Rest of World)

[contact] (Phone for North America)

[name] (Fax for Rest of World)

[contact] (Fax for North America)

[contact] (email)

The **minimum** information required on the SAE report is:

- Protocol number;
- Centre number or Investigator name;
- Subject number;
- An AE or outcome that can be identified as serious;
- A suspected investigational product;
- Investigator's or Co-Investigator's assessment of relationship to the investigational product;
- Name and signature of reporter.

Follow-up information must be actively sought and submitted as soon as it becomes available.

All serious, unexpected and related AEs (SUSARs) must also be reported to the reviewing Institutional Review Board (IRB)/Independent Ethics Committee (IEC) according to local and national requirements. Circassia Ltd will provide details to other Investigators of such AEs for this purpose.

Reports relating to the subject's subsequent medical course must be submitted to the Sponsor until the event has subsided or, in the case of permanent impairment, until it stabilises and the overall clinical outcome has been ascertained. The Investigator will also provide additional information, including a copy of the following documents (where applicable):

- Copies of all test results;
- Hospital discharge summary (as soon as it is available to the Investigator);
- Autopsy report (as soon as it is available to the Investigator).

SAEs that come to the attention of the Investigator at any time up until the end of the study (Visit 5) must be reported to the Sponsor in the same manner as a SAE occurring during the dosing period.

The Investigator will notify the IRB/IEC of all SAEs that occur during this study, if required by local or national laws and regulations.

The appropriate regulatory authority will be notified of all SUSARS within the required reporting timelines.

#### 6.4.3 Reporting of Pregnancy

Subjects who become pregnant before the start of dosing (from consent to Visit 3A) must be withdrawn from study immediately after the pregnancy is confirmed. Subjects who become

VERSION FINAL4.0 CONFIDENTIAL PAGE 61 OF 92

pregnant during the dosing period must receive no further study treatment and the pregnancy must be reported using the same procedure as for SAEs (see Section 6.4.2). Subjects who become pregnant once dosing has completed may remain in the study and the pregnancy must be reported using the same procedure as for SAEs. Pregnancy will be recorded in the subject's medical files. A Pregnancy Notification Form must be completed and is reported using the same procedure as for the SAEs (see Section 6.4.2). The outcome of the pregnancy will be followed-up until term end, full or premature termination. A Pregnancy Outcome Form, to assess the health of the mother and any infants, will be completed and reported following the same procedure as the notification form.

## 6.4.4 Safety Evaluations

## 6.4.4.1 Demographic and Medical History

The demographic data and a complete medical history with an emphasis on allergy including rhinoconjunctivitis and asthma will be recorded at Screening (Visit 1B/C). This will include skin prick testing to HDM.

## 6.4.4.2 Physical Examination

A physical examination will be conducted at Screening (Visit 1B/C), at the End of Dosing Assessment (Visit 3I) and at the Period 3 Follow-Up (Visit 5). At Screening this will be a full examination comprising:

- Eye, ears, nose, throat, neck, including a check for nasal polyps;
- Respiratory system;
- Central and peripheral nervous system;
- Cardiovascular system;
- Gastrointestinal system (including the mouth);
- Musculoskeletal system;
- Skin;
- Lymph node palpation;
- Other systems if abnormality is suspected.

At visits 3I and 5 the physical examination will be a targeted exam, with organ systems examined if the medical history or AEs indicate a reason for examination.

#### 6.4.4.3 Vital Signs

Blood pressure, pulse rate, respiratory rate and body temperature will be recorded at Screening (Visit 1B/C), prior to and 30 minutes after Study Medication Administration

VERSION FINAL4.0 CONFIDENTIAL PAGE 62 OF 92

(Visits 3A-3H), at the End of Dosing Assessment (Visit 3I), at each PAC visit and at Period 3 Follow-Up (Visit 5). Measurements will be made with the subjects rested and in the sitting or semi-recumbent position.

## 6.4.4.4 Laboratory Assessments

Blood samples using the Vacutainer® system for haematology and biochemistry tests and urine samples for urine dipstick tests will be obtained at Screening (Visit 1B/C), at the End of Dosing Assessment (Visit 3I) and at the Period 3 Follow-Up (Visit 5).

Blood samples for Der p, Der f and perennial allergen specific IgE will be obtained at Screening (Visit 1A) and will be measured by ImmunoCAP®. At the End of Dosing Assessment (Visit 3I) and at Period 3 Follow-Up (Visit 5) blood samples for Der p and Der f specific IgE, measured by ImmunoCAP®, will be obtained.

A blood sample will be taken at screening only for measurement of a fixed panel of Der p allergens using an immune-affinity based analysis technology such as ImmunoCAP®.

Urine samples for pregnancy tests will be collected from FOCBP and analysed immediately at Screening (Visit 1B/C), before dosing at Study Medication Administration Visits (Visits 3A-3H), at the End of Dosing Assessment (Visit 3I) and at Period 3 Follow-Up (Visit 5).

The following parameters will be measured:

Haematology: haematocrit, haemoglobin, red blood cells, white blood cells (WBC),

WBC differentials (neutrophils, eosinophils, basophils, lymphocytes,

monocytes) and platelets.

Biochemistry: sodium, potassium, chloride, urea, creatinine, calcium, phosphorus,

total protein, albumin, uric acid, total bilirubin, glucose (random), lactate dehydrogenase, creatine phosphokinase, alanine transaminase, aspartate transaminase, gamma glutamyltransferase, and alkaline

phosphatase;

Blood samples will be collected for assay of tryptase in the case of a

suspected anaphylactic response [see Section 6.2.2]).

Urine dipstick: pH, protein, ketones, blood and glucose.

Immunology: Der p, Der f and relevant perennial allergen specific IgE (measured by

ImmunoCAP®).

Additional tests may be performed if clinically warranted. Abnormal values should be followed up they have returned to normal or an adequate explanation has been established.

All laboratory test reports must be reviewed, signed and dated by the Investigator or delegated physician. Reports will then be filed with the subject's medical record. The Investigator will comment on all abnormal results and determine whether it is clinically significant. These assessments will be recorded in the eCRF.

Any clinically significant abnormal laboratory value constitutes an AE and must be recorded as an AE in the eCRF. For grading an abnormal value or result of a clinical or laboratory evaluation, Investigators are encouraged to consult National Cancer Institute's Common Terminology Criteria for Adverse Events (CTCAE) Version 4.0. A value that increases by one grade from baseline or from the last post-baseline value that does not meet grading criteria should ordinarily be considered clinically relevant and hence reported as an adverse event. A CTCAE grade increase of one in clinical or laboratory evaluation will translate to 'mild' in the above grading, an increase of two will be 'moderate' and an increase of three or more will be 'severe'. For additional information and a printable version of the manual, consult the NCI-CTCAE web site: http://ctep.cancer.gov/reporting/ctc.html.

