### **16.1.1. ALL TEAEs**

#### **16.1.1.1. Severity**

Severity is classed as mild/moderate/severe (increasing severity). TEAEs with a missing severity are to be classified as severe. If a subject reports a TEAE more than once within that SOC/PT, the AE with the worst case severity is to be used in the corresponding severity summaries.

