**16.3. LABORATORY EVALUATIONS**

Results from the central laboratory are to be included in the reporting of this study for Haematology, Biochemistry, Urine dipstick and Immunology. Quantitative laboratory assessments are to be summarised by descriptive statistics and presented in International System of Units (SI). Categorical assessments are to be presented by frequency (n) and percentage (%) of subjects.

---

Document: TH005 SAP Version 2.docx

Author: [name]

Version Number:

2.0

Version Date:

24MAR2017

Template No: CS\_TP\_BS016 – Revision 3

Effective Date: 01May2012

Reference: CS\_WI\_BS005

Copyright © 2012 Quintiles Transnational Corp. All rights reserved.

The contents of this document are confidential and proprietary to Quintiles Transnational Corp. Unauthorized use, disclosure or reproduction is strictly prohibited.

---

Quantitative laboratory assessments reported as “< X”, i.e. below the lower limit of quantification (BLQ), or “> X”, i.e. above the upper limit of quantification (ULQ), are to be converted to X for the purpose of quantitative summaries, but are to be presented as recorded, i.e. as “< X” or “> X” in the listings.

The following summaries are to be provided for laboratory data:

- Actual and change from Baseline by visit (for quantitative measurements)
- Shift from Baseline according to normal reference range criteria (for quantitative measurements and categorical measurements) by visit
- Listings of all laboratory assessments

The following assessments are to be measured and presented:

- Haematology: Haematocrit, haemoglobin, red blood cells, white blood cells (WBC), WBC differentials (neutrophils, eosinophils, basophils, lymphocytes, monocytes) and platelets
- Biochemistry: Sodium, potassium, chloride, urea, creatinine, calcium, phosphorus, total protein, albumin, uric acid, total bilirubin, glucose (random), lactate dehydrogenase, creatine phosphokinase, alanine transaminase, aspartate transaminase, gamma glutamyltransferase and alkaline phosphatase
- Urine dipstick: pH, protein, ketones, blood and glucose
- Immunology: All relevant perennial allergen specific IgE
- Tryptase for anaphylactic response

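### For subjects who enter with a graded laboratory abnormality, AE severity follows the number of CTCAE grades gained, not the grade reached, so a rise from baseline grade 2 to 3 or 3 to 4 is recorded as mild

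*Protocol*

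**What the plan says.** Protocol section 6.4.4.4 makes every clinically significant abnormal laboratory value an adverse event. For grading, "Investigators are encouraged to consult National Cancer Institute's Common Terminology Criteria for Adverse Events (CTCAE) Version 4.0". The trigger for reporting is "A value that increases by one grade from baseline or from the last post-baseline value that does not meet grading criteria", which is ordinarily to be treated as clinically relevant. Severity is then assigned by conversion: "A CTCAE grade increase of one in clinical or laboratory evaluation will translate to 'mild' in the above grading", and "an increase of two will be 'moderate' and an increase of three or more will be 'severe". The conversion does not mention the grade reached and makes no exception for a subject who already has a graded value at baseline.

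The grading it refers back to is the three-level scale under Severity in Protocol section 6.4.1. That scale describes the effect of the event on the subject; its top level reads "Incapacitating with inability to perform usual activities".

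The SAP uses the recorded category. Section 16.1 has an overview line for severe TEAEs. Section 16.1.1.1 ("Severity is classed as mild/moderate/severe (increasing severity") tabulates the worst recorded severity for each subject within system organ class and preferred term. Nothing in the SAP derives severity from laboratory data. The laboratory summaries in section 16.3 are values and changes by visit and "Shift from Baseline according to normal reference range criteria", with low, normal and high as the only categories for quantitative tests (section 16.3.1).

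**The concern.** A severity label should let a reader compare events across subjects. Here two subjects with the same grade 3 value can be labelled severe (baseline grade 0) and mild (baseline grade 2). The difference always runs downward, and it falls on subjects who entered with an abnormality that then worsened.

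Nothing at entry rules such subjects out. Bloods are taken at Screening, but no inclusion or exclusion criterion in Protocol sections 4.2 and 4.3 sets a laboratory limit. Exclusion 21 rests on history or physical findings and the investigator's opinion.

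The planned categorical tables would not recover the information. A subject already above the reference range at baseline who worsens to grade 4 appears in the shift table as high to high, which is no shift. No planned table shows CTCAE grade. Someone scanning the severe TEAE line or the worst-severity tables would miss these events.

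**Working it through.** There is no stated figure to reproduce. The check applies the conversion rule to every possible rise.

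**Inputs**
- Rule (Protocol 6.4.4.4): rise of 1 = mild, 2 = moderate, 3 or more = severe.
- Reference point (same section, trigger sentence): baseline, or the last post-baseline value that met no grade. The conversion sentence does not restate it; I assume the same reference applies.
- Grade range 0 to 4, with 0 meaning no grade met. This is an assumption, since the documents do not reproduce the CTCAE scale.

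**Formula**

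Rise = grade reached − baseline grade; severity is read from the rise.

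| Grade reached | Baseline 0 | Baseline 1 | Baseline 2 | Baseline 3 |
|---|---|---|---|---|
| 1 | 1 − 0 = 1, mild | | | |
| 2 | 2 − 0 = 2, moderate | 2 − 1 = 1, mild | | |
| 3 | 3 − 0 = 3, severe | 3 − 1 = 2, moderate | 3 − 2 = 1, mild | |
| 4 | 4 − 0 = 4, severe | 4 − 1 = 3, severe | 4 − 2 = 2, moderate | 4 − 3 = 1, mild |

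**Counts**
- All rises: 4 + 3 + 2 + 1 = 10. From baseline 0: 4. From a non-zero baseline: 3 + 2 + 1 = 6.
- Compare each of the 6 with the baseline 0 entry in its row. Five are lower: 1 to 2 (mild against moderate), 1 to 3 (moderate against severe), 2 to 3 (mild against severe), 2 to 4 (moderate against severe) and 3 to 4 (mild against severe). One agrees: 1 to 4. None is higher.
- Grade 3 can therefore be mild, moderate or severe according to the starting grade alone, and so can grade 4.

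**Section 6.4.4.4 against the severity definitions in section 6.4.1**

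The two can disagree in either direction. A symptomless rise from grade 0 to 3 is severe by the conversion rule, but it does not incapacitate anyone. A rise from baseline grade 2 to 3 that interferes with usual activities and needs added therapy is mild by the conversion rule and moderate by the definitions. The protocol does not say which governs.

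**The case against.** Several points on the other side have force.

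- **The rule has a rationale.** Section 6.4.1 counts exacerbation of an existing illness as an AE and leaves out pre-existing conditions that do not worsen. For a subject abnormal at entry the event is the worsening, and the rule grades its size. This explains the trigger. It does not justify giving the same word to 0 to 1 and 3 to 4.
- **CTCAE is only encouraged.** Consulting it is, and one-grade rises are only ordinarily reported. The conversion sentence itself is unconditional. If some sites apply it and others use the functional definitions, severity becomes inconsistent between sites.
- **Few subjects.** This stands. The clearest mislabels need a baseline of grade 2 or 3, exclusion 21 removes significant disease in the investigator's opinion, and routine bloods are scheduled only twice after Screening (Visits 3I and 5).
- **Limited consequence.** This also stands. The primary safety endpoint (Protocol 7.5.4) counts AEs and subjects with AEs, which severity does not change. Safety is descriptive, seriousness is judged separately (section 6.4.2), and individual laboratory values are listed with out-of-range results marked.
- **Clinical evaluations.** The rule names these too, but injection-site and systemic allergic reactions have their own scales by grade reached (Table 7 and Appendix 4), which narrows its reach.

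A reader might go further, and the documents do not support it:

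- *Any move from grade 2 to 3 is mild.* No. Counted from baseline, a subject who goes from 0 through 2 to 3 on study has risen three grades and is severe.
- *Five in six such events are mislabelled.* No. The ratio weights possible transitions equally, and the documents give no distribution of baseline grades.
- *Section 6.4.1 already grades by laboratory level, and the conversion rule breaks it.* No. It is a functional scale, so a rule based on the grade reached also differs from it and must be reconciled.

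**Conclusion.** Wrong as written, with minor impact. For subjects whose baseline value already meets grade 1 or higher, the conversion labels 5 of 6 possible rises below the label for the same grade reached from baseline 0, including 2 to 3 and 3 to 4 as mild. All rises from baseline 0 are unaffected. This rests on a 0–4 scale and on counting the rise from baseline. The documents do not allow an estimate of how many events are involved; the number is probably small.

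The effect is confined to the severe TEAE line and the severity tables. AE counts and SAE reporting are unaffected. Separately, section 6.4.4.4 and the severity definitions in section 6.4.1 can give different categories for one event, and the two passages must be reconciled.

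**What to change.** 1. In Protocol section 6.4.4.4, or the eCRF completion guidance, keep the one-grade rise as the trigger for reporting. Base the severity of laboratory AEs on the grade reached: 1 mild, 2 moderate, 3 or higher severe. The present rule already gives this mapping from a grade 0 baseline.
2. State how this relates to the functional definitions in section 6.4.1, including which governs when they differ and whether the conversion still applies to clinical evaluations.
3. For AEs already entered, do not overwrite the investigator's severity, and do not re-derive it by program. Either query discrepant laboratory AEs before database lock, while the study is still blinded, or add a supplementary listing or shift table by CTCAE grade reached.

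The cost is a sentence or two of text, plus either a set of queries or one extra output. The extra output needs the CTCAE thresholds to be programmed, since neither document contains them. The count of severe laboratory AEs may rise slightly.
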